### 3.2.2 Secondary Outcome Measures

1. All antibiotic use from Day 1 through Day 11 and from Day 1 through Day 28 in each treatment group
2. The proportion of subjects with one or more unplanned return visits to a physician's office or urgent care for persistent or worsening LRTI from Day 1 through Day 11 and from Day 1 through Day 28 in each treatment group
3. The proportion of subjects with one or more emergency department visits for persistent or worsening from Day 1 through Day 11 and from Day 1 through Day 28 in each treatment group
4. The proportion of subjects with one or more hospitalizations for persistent or worsening LRTI (if not hospitalized at the enrollment visit) from Day 1 through Day 11 and from Day 1 through Day 28 in each treatment group
5. The proportion of subjects exhibiting improvement in at least one presenting symptom at Day 11 and at Day 28 in each treatment group
6. The efficacy of azithromycin versus placebo on Day 11 will be based on clinical improvement. Clinical improvement will be defined as fulfillment of **all** the following criteria:
  - For subjects who qualified based on the presence of at least two symptoms, then improvement must be observed in at least two symptoms present at enrollment (i.e., cough, sputum production, chest pain, difficulty breathing, or fever). For subjects who qualified based on the presence of one symptom and at least one vital sign abnormality, improvement must be observed in the one symptom present at enrollment. For symptoms other than fever, at least a one-step improvement (e.g., improvement from moderate to mild cough) will be considered a clinical improvement (Table 1).
  - **Note:** fever will be objectively ( $\geq 37.8$  °C or 100.0 °F, measured anywhere on the body) or subjectively reported by the subject for the day preceding or on the Day 11 visit. For Day 11, fever will be used similar to what has been done for Day 5 outcome measure definition i.e. clinical improvement requires absence of fever in the day preceding or at the Day 11 Visit.
  - **Note:** vital signs were not recorded at Days 11 and 28. Therefore, the subcomponents of clinical improvement at Day 11 and 28 are different from the subcomponents of clinical improvement used for the primary outcome measure at Day 5 (i.e., subcomponents at Day 11 and 28 do not include any reference to vital signs measures).

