3.3.3. Clinical Improvement at D11V

Clinical improvement at D11V is defined as fulfillment of **all** the following criteria:

- For subjects who qualified based on the presence of at least two symptoms, then improvement must be observed in at least two symptoms present at enrollment (i.e., cough, sputum production, chest pain, difficulty breathing, or fever). For subjects who qualified based on the presence of one symptom and at least one vital sign abnormality, improvement must be observed in the one symptom present at enrollment. For symptoms other than fever, at least a one-step improvement (e.g., improvement from moderate to mild cough) will be considered a clinical improvement.
- **Note:** fever will be objectively (≥37.8 °C or 100.0 °F, measured anywhere on the body) or subjectively reported by the subject for the day preceding or on the D11V. For Day 11, fever will be

used similar to what has been done for Day 5 outcome measure definition i.e. clinical improvement requires absence of fever in the day preceding or at the D11V.

- **Note:** vital signs were not recorded at Days 11 and 28. Therefore, the subcomponents of clinical improvement at D11V and D28V are different from the subcomponents of clinical improvement used for the primary outcome measure at D5V (i.e., subcomponents at D11V and D28V do not include any reference to vital signs measures).
- Absence of deterioration in any qualifying symptom (i.e., cough, sputum production, chest pain, difficulty breathing, or fever). For symptoms other than fever, at least a one-step deterioration (e.g. worsening from mild to moderate cough) will be considered clinical deterioration.
- No medically attended visit to an ambulatory medical facility (e.g., ED, outpatient clinic, urgent care center) or hospitalization for persistent or worsening LRTI at any time after randomization (persistent or worsening LRTI is defined as receipt of a non-study antibiotic [parenteral or oral] treatment for LRTI or its complication). **Note:** receipt of a non-study antibiotic after study day 11 will not be regarded as satisfying this definition if it is related to a new non-respiratory process that is unrelated to the prior diagnosis of LRTI.

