6.5.2. Clinical Improvement at D11V and D28V

Clinical improvement at D11V is defined as fulfillment of all the following 1) For subjects who qualified based on the presence of at least two symptoms, then improvement must be observed in at least two symptoms present at enrollment (i.e., cough, sputum production, chest pain, difficulty breathing, or fever). For subjects who qualified based on the presence of one symptom and at least one vital sign abnormality, improvement must be observed in the one symptom present at enrollment 2) Absence of deterioration in any qualifying symptom (i.e., cough, sputum production, chest pain, difficulty breathing, or fever); or new vital sign abnormality not present at enrollment 3) No medically attended visit to an ambulatory medical facility (e.g., ED, outpatient clinic, urgent care center) or hospitalization for persistent or worsening LRTI at any time after randomization. Persistent or worsening LRTI is defined as receipt of a non-study antibiotic [parenteral or oral] treatment for LRTI or its complication. However, receipt of a non-study antibiotic after study day 11 will not be regarded as satisfying this definition for D11V if it is related to a new non-respiratory process that is unrelated to the prior diagnosis of LRTI.

Subjects will be assessed on whether they were enrolled based on at least two qualifying symptoms (cough, sputum production, chest pain, or difficulty breathing) or based on one qualifying symptom and one abnormal vital sign. Severity recorded on the LRTI Symptoms and Fever form (LRT) for Visit 1 will be used as baseline. Symptoms severity for D11V will be obtained from the solicited events form (LRS) for the event date corresponding to the date of study day 11. Symptoms severity for D28V will be obtained from LRT form for Visit 5. Vital signs were not recorded for D11V and D28V.

6.5.2.1. Improvement in Two Symptoms or One Symptom Present at Enrollment at D11V and D28V

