For subjects who qualified based on two symptoms, improvement in symptoms at D11V or D28V will be defined as presence of at least one-step improvement in two qualifying symptoms present at enrollment. For subjects who qualified based on one symptom and one vital sign abnormality, clinical improvement at D11V or D28V will be defined as the presence of at least one-step improvement in the one symptom present at baseline. If the one qualifying symptom at baseline has a missing value at D11V or D28V, then improvement in symptoms at D11V or D28V is missing, respectively.

Improvement in fever at D11V or D28V is defined as changing from presence of fever at baseline to absence of fever on D11V or D28V, respectively. Fever will be present at D11V if temperature reported on the LRS form for study day 11 is $\geq 100.0^{\circ}\text{F}$ or if subjective fever is recorded on the LRS form on study day 11. A subject has fever at baseline or at D28V if the subject had subjective fever or a temperature of $\geq 100.0^{\circ}\text{F}$ reported on the LRT form (i.e. LRTTMPF ≥ 100 or LRTFEVYN = Yes) for Visit 1 or Visit 5, respectively. If

at least some of the temperature information is available at D11V or D28V, but none of it indicates objective or subjective fever, then fever is absent at D11V or D28V respectively. If none of the temperature or fever information is available at D11V or D28V, then fever is missing at D11V or D28V, respectively.

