8.3.8. New occurrence of Fever at D11V Using ATP-11 Analysis Population

Using ATP-11, a forest plot of 95% CIs for the risk difference of fever in the 24 hours preceding or at D11V will be provided in [Figure 15](#). Results of fever at D11V will also be reported in [Table 45](#). Tests for differences in proportions between treatment arms will be given by Fisher's exact tests. The Miettinen–Nurminen method will be used to compute all 95% CIs for risk differences.

8.3.9. Bivariate Analysis of DOOR and Number of Days of Antibiotics Use at D5V and D11V

In addition to the DOOR analyses described in Section 8.2.8, a two-dimensional analysis of the DOOR probability and difference in the mean duration of antibiotic use in the two treatment groups will also be performed at D5V. Only subjects with non-missing DOOR and number of days on antibiotics will be included in these analyses. The horizontal axis is the DOOR probability (probability of a more desirable outcome when assigned to placebo vs. azithromycin) based on the ordinal DOOR outcome ignoring the duration of antibiotic use. The vertical axis is the difference in the means of the observed (outcome not assignment) duration of antibiotic use (placebo minus azithromycin). A result in the lower right quadrant represents more desirable results for placebo, while a result in the upper left represents more desirable for azithromycin. The other two quadrants represent tradeoffs for clinical outcomes and antibiotic use.

1000 bootstrap samples will be generated by resampling with replacement from the empirical distribution of DOOR and number of days of antibiotics use at D5V. The DOOR probability and mean difference in the number of days of antibiotics use will be estimated using the bootstrap samples and plotted as a scatter plot. A 95% joint region of DOOR probability and duration for antibiotic will be constructed first using a parametric method and repeated using a nonparametric method. The parametric method will estimate the confidence region using the ellipse method from the CAR R package which uses a bivariate normal distribution. The nonparametric will use distribution-free approach implemented in the distfree.cr R package proposed by Hu and Yang (2013) in [12]. Marginal distributions of DOOR probability and difference in duration of antibiotics will be provided. To confirm the robustness of these results, these plots will be regenerated using 2000

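### The SAP's Day 11 derivation omits the fever-free condition that the protocol and SAP 3.3.3 require, and reads fever on study day 11 only

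*SAP*

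**What the plan says.** **The definition.** Protocol 3.2.2, item 6, says that fever is handled at Day 11 as it is at Day 5: "clinical improvement requires absence of fever in the day preceding or at the Day 11 Visit". SAP 3.3.3 repeats this: "clinical improvement requires absence of fever in the day preceding or at the D11V". Both state a condition of success with a two-day window.

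**The derivation.** SAP 6.5.2 lists three criteria for Day 11:

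1. Symptom improvement. For subjects who entered on two symptoms, SAP 6.5.2.1 asks for "at least one-step improvement in two qualifying symptoms present at enrollment". For subjects who entered on one symptom plus a vital sign, improvement in that one symptom suffices. Fever is treated as an item that can improve: "Improvement in fever at D11V or D28V is defined as changing from presence of fever at baseline to absence of fever on D11V or D28V".
2. "Absence of deterioration in any qualifying symptom (i.e., cough, sputum production, chest pain, difficulty breathing, or fever"), to which SAP 6.5.2 adds new vital sign abnormalities.
3. No medically attended visit or hospitalization for persistent or worsening LRTI.

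Fever itself is read from one form and one day: "Fever will be present at D11V if temperature reported on the LRS form for study day 11 is" at or above 100.0 °F, "or if subjective fever is recorded on the LRS form on study day 11".

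**Elsewhere in the SAP.** SAP 3.3.1 lets the Day 11 visit fall on Day 11 to Day 14. SAP 8.3.8 plans "a forest plot of 95% CIs for the risk difference of fever in the 24 hours preceding or at D11V", and the Day 11 DOOR imputation model in SAP 8.4.2 also uses a fever variable that reaches back to the previous day.

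**The concern.** SAP 6.5.2 gives the form-level rules that a programmer would code, and they do not produce the endpoint that the protocol and SAP 3.3.3 define. The Day 5 endpoint shows what is missing: SAP 6.5.1 lists absence of fever as its third criterion, and SAP 6.5.1.3 gives it sources, a two-day window and a missing-data rule. Day 11 has no counterpart.

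Day 11 clinical improvement is tested for non-inferiority against the 12.5% margin in the ITT and ATP-11 populations, and it feeds the Day 11 ordinal clinical outcome and DOOR. In a trial of withholding an antibiotic, lasting fever is one of the ways in which the placebo group could do worse. An endpoint that counts some febrile subjects as improved is less able to register that.

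**Working it through.** The plan states no figure to reproduce here. The check sets the two rules against each other.

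**Step 1. Visit on Day 11.** Take a subject with two improved non-fever symptoms, no other deterioration and no medically attended visit. Assume that fever deterioration means absent at baseline and present on study day 11; SAP 6.5.2.2 does not say so.

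- Definition (Protocol 3.2.2, SAP 3.3.3): improved only if there is no fever on Day 10 and none on Day 11.
- Derivation (SAP 6.5.2): improved unless fever is absent at baseline and present on Day 11.

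| Fever at baseline | Day 10 | Day 11 | Definition | Derivation |
|---|---|---|---|---|
| no | no | no | improved | improved |
| no | no | yes | not | not |
| no | yes | no | not | **improved** |
| no | yes | yes | not | not |
| yes | no | no | improved | improved |
| yes | no | yes | not | **improved** |
| yes | yes | no | not | **improved** |
| yes | yes | yes | not | **improved** |

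The rules disagree in 4 of 8 patterns, each time because the derivation counts as improved a subject whom the definition does not. The last row is persistent fever. The count is of patterns, not of subjects, so it is not a rate.

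**Step 2. The missing criterion alone.** Hold the fever window the same under both rules. Leaving out a necessary condition can only turn failures into successes. Let q_P and q_A be the shares of placebo and azithromycin subjects who are febrile in the window yet meet all three SAP 6.5.2 criteria. Then

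derived difference (placebo − azithromycin) = defined difference + (q_P − q_A).

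Equal shares leave the difference unchanged. A larger share on placebo moves the result toward non-inferiority, and a larger share on azithromycin moves it away.

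**Step 3. The window alone.** Now let the call take place on Day 13.

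- Subject A has no fever at baseline, fever on study day 11, and none on Days 12 and 13. The derivation records a deterioration and a failure. The definition looks at Days 12 and 13 and finds no fever.
- Subject B entered on two symptoms, with fever at baseline, and has one other symptom improved. Fever is present on study day 11 and absent on Days 12 and 13. The derivation counts one improved item and fails the subject. The definition counts fever as improved too, which makes two, and finds the subject fever-free.

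Both errors run toward failure, whereas the third row of the table (fever on Day 10 only) runs toward success. The window can therefore err either way. Errors toward failure of this kind need a call on Day 13 or 14, because for a call on Day 12 the previous day is Day 11 itself.

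**The case against.** The strongest reply is that SAP 3.3 holds the study definitions, SAP 3.3.3 keeps the requirement intact, and SAP 6.5.2 sits under Missing Data, so the definition should govern. That is fair as far as it goes: the SAP has not abandoned the rule, and this is a contradiction between its sections. But the SAP states no order of precedence, and 6.5.2 restates the criteria as a complete list and names the forms. The new-vital-sign wording in its second criterion does not rescue it, because that reaches only new abnormalities and the same section says vital signs were not recorded at Day 11.

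A reader might also infer three stronger things that the documents do not support.

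- *That the whole discrepancy favors success.* Only the missing criterion does. Step 3 shows the window erring the other way.
- *That excess fever on placebo would be hidden.* SAP 8.3.8 and Table 45 report Day 11 fever by arm with a confidence interval and a test, and Table 35 reports improvement in fever by arm. The information would be missing from the composite but not from the report, at least in ATP-11.
- *That a known part of the margin is at risk.* Shares of 4% on placebo and 1% on azithromycin would give 4 − 1 = 3 of the 12.5 points, but neither document gives a Day 11 fever rate. Nor is the febrile share the misclassified share: those subjects must also meet the other criteria, and new fever on study day 11 already fails if deterioration means absent to present.

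Finally, SAP 8.1.1 lets only the primary analysis establish non-inferiority and treats the others as supportive. That limits the weight of the point but does not remove the contradiction.

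**Conclusion.** The point holds in limited form. SAP 6.5.2 to 6.5.2.2 contradicts Protocol 3.2.2 (item 6) and SAP 3.3.3: it has no Day 11 fever-free criterion, and it reads fever on study day 11 whatever the visit date. The first defect misclassifies only toward success; the second can go either way.

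The reach is the secondary Day 11 non-inferiority analyses (ITT and ATP-11) and the Day 11 ordinal outcome and DOOR. The primary analysis is unaffected because Day 5 has its full fever rule. Day 28 is unaffected because the fever-free sentence is written for Day 11 only.

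The size cannot be computed. It depends on q_P − q_A and on how many calls fell after Day 11, and the documents give neither. The enumeration rests on reading fever deterioration as absent to present, which the SAP should state.

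**What to change.** Add to SAP 6.5.2 a Day 11 absence-of-fever criterion parallel to 6.5.1.3, and list it among the Day 11 criteria:

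- A temperature of 100.0 °F or more, or subjective fever, on the date of the Day 11 visit or the day before it, from the LRS form or the temperature collected at the Visit 4 call, means clinical improvement is No.
- If some fever information is available and none of it shows fever, fever is absent.
- If no fever information is available, absence of fever is missing. It should not be coded as failure.

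In the same edit:

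- Define fever deterioration as absent at baseline and present at the Day 11 visit.
- State whether the anchor is the visit date or study day 11, and use the same anchor for symptoms. SAP 6.5.2 now takes symptoms on study day 11, so moving fever alone would create a new mismatch.
- State which form supplies Days 12 to 14. Protocol 8.1 runs the memory aid through Visit 4, but SAP 9.3.1 describes solicited-event recording for Days 1 to 11 only.

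The cost is a short SAP revision and a change to one derived variable. No new data collection is foreseen: Protocol 7.3.3 already collects temperature at the Day 11 call, and Protocol 8.1 documents the maximum over the preceding 24 hours at each follow-up visit.

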6.5.2.2. Absence of Deterioration in Any Qualifying Symptoms at D11V or D28V

Clinical deterioration at D11V or D28V is defined as the deterioration in any qualifying symptoms (i.e., cough, sputum production, chest pain, difficulty breathing, or fever). For symptoms other than fever, clinical deterioration will be determined as the presence of at-least one step deterioration (worsening from mild to moderate) in any qualifying symptom regardless whether the symptom was present at enrollment or not. If at least one of the symptoms has a missing value at D11V or D28V and none of the observed parameters deteriorated, absence of deterioration will be missing at the corresponding visit. If none of the observed symptoms deteriorated and none of them had a missing value, then there is absence of deterioration. If at least one observed symptom deteriorated at study day 11, then there is no absence of deterioration at D11V regardless of whether any parameter has a missing value. Similarly, if at least one observed symptom deteriorated at D28V, then there is no absence of deterioration at D28V regardless of whether any parameter has a missing value.

6.5.2.3. No Medically Attended Visit or Hospitalization for Persistent or Worsening LRTI at Any Time Post Randomization at D11V and D28V

No Medically Attended Visit (MAV) to an ambulatory medical facility (e.g., ED, outpatient clinic, urgent care center) or hospitalization for persistent or worsening LRTI at any time after randomization (persistent or worsening LRTI is defined as receipt of a non-study antibiotic [parenteral or oral] treatment for LRTI or its complication). Note that receipt of a non-study antibiotic after D11V study day will not be regarded as satisfying this definition if it is related to a new non-respiratory process that is unrelated to the prior diagnosis of LRTI. Medically Attended visit information will be recorded on the MAV form. No MAV or hospitalization for persistent or worsening LRTI will then be derived as follows:

- If MAVWSCP = 'Y' and (MAVABRX = 'Y' and (MAVA1RTI = 'Y' or MAVA2RTI = 'Y' or MAVA3RTI = 'Y')), then MAV or Hospitalization for persistent or worsening LRTI at D11V is present.
- If MAVBRX='N' or (MAVABRX = 'Y' and (MAVA1RTI ^= 'Y' and MAVA2RTI ^= 'Y' and MAVA3RTI ^= 'Y')), then MAV or Hospitalization for persistent or worsening LRTI at D11V is absent.
- If a subject did not complete D11V and had no MAV submitted, then MAV or Hospitalization for persistent or worsening LRTI at D11V is missing.
- Otherwise, if a subject completed D11V but had no MAV submitted then MAV or Hospitalization for persistent or worsening LRTI at D11V is absent.

Similar derivations will be used for D28V by replacing D11V by D28V.

6.5.3. Most Severe Solicited Event for DOOR

If a subject had severity grades (0 to 3) recorded for every solicited event (abdominal pain, vomiting, diarrhea, allergic reaction, and candidiasis) from Study day 1 to D5V Study day, inclusive, then the most severe solicited event at D5V, a component of DOOR, will be the maximum severity grade taken across all solicited events from Study Day 1 to D5V Study Day.

If a subject had any solicited event of severity grade 3 from Day 1 to D5V Study Day, then the most severe solicited event at D5V will be grade 3, regardless of the presence of missing data during that period. Otherwise, if the subject has missing data for the severity grade of any solicited event from Day 1 to D5V study day, then most severe solicited event at D5V will be missing.

If a subject had severity grades (0 to 3) recorded for every solicited event (abdominal pain, vomiting, diarrhea, allergic reaction, and candidiasis) from study day 1 to study day 11, inclusive, then the most severe solicited event at D11V, a component of DOOR at D11V, will be the maximum severity grade taken across all solicited events from study day 1 to study day 11.

If a subject had any solicited event of severity grade 3 from Day 1 to study day 11 study day, then the most severe solicited event at study day 11 will be grade 3, regardless of the presence of missing data during that period. Otherwise, if a subject has missing data for the severity grade of any solicited event from Day 1 to study day 11 study day, then most severe solicited event at D11V will be missing.

A similar approach as described above will be used to determine the most severe solicited event at D28V by considering all solicited events reported post dose 1.

